## 17.4 Secondary endpoints

### 17.4.1 Confirmatory secondary endpoints

If efficacy of mealtime faster-acting insulin aspart can be confirmed in the primary analysis, the trial also aims to compare treatment arms for a number of confirmatory secondary endpoints. The family-wise type I error rate will be controlled in the strong sense using a hierarchical (fixed sequence) testing procedure. This is based on a priority ordering of the null-hypotheses, and testing them in this order using the two-sided 95% confidence interval approach until an insignificant result appears. The effect is that rejection of the null hypothesis only, will be confirmed for endpoints where all previous null-hypotheses have been rejected in favour of faster-acting insulin aspart.

The steps in the hierarchical testing procedure are:

**Step 1 (Primary analysis):** Change from baseline in HbA1c after 26 weeks of treatment (non-inferiority of mealtime faster-acting insulin aspart versus mealtime NovoRapid®)

**Step 2:** Change from baseline in HbA1c after 26 weeks of treatment (non-inferiority of postmeal faster-acting insulin aspart versus mealtime NovoRapid®)

**Step 3:** Change from baseline in 1-hour PPG increments after 26 weeks of treatment (meal test) (superiority of mealtime faster-acting insulin aspart versus mealtime NovoRapid®)

**Step 4:** Change from baseline in 1,5-Anhydroglucitol after 26 weeks of treatment (superiority of mealtime faster-acting insulin aspart versus mealtime NovoRapid®)

**Step 5:** Change from baseline in HbA1c after 26 weeks of treatment (superiority of mealtime faster-acting insulin aspart versus mealtime NovoRapid®)

#### Change from baseline in HbA1c after 26 weeks of treatment (step 2)

Step 2 in the hierarchical testing procedure is to confirm efficacy of treatment with postmeal faster-acting insulin aspart in terms of glycaemic control by showing that postmeal faster-acting insulin aspart is non-inferior to NovoRapid® both in combination with insulin degludec in terms of glucose lowering effect as assessed by change from baseline in HbA1c after 26 weeks of treatment using a non-inferiority margin of 0.4%.

The non-inferiority will be evaluated as described in section [17.3](#) based on a two-sided 95% confidence interval of mean treatment difference (postmeal faster-acting insulin aspart minus mealtime NovoRapid®) obtained from the primary statistical analysis.

The sensitivity of the analysis will be addressed as described in section [17.3](#).

### **Change from baseline in 1-hour PPG increments after 26 weeks of treatment (meal test) (step 3)**

As the third step of the hierarchical testing procedure changes from baseline in 1-hour PPG increments (meal test) after 26 weeks of treatment will be tested for superiority of mealtime faster-acting insulin aspart compared to mealtime NovoRapid®.

The 1-hour PPG increment will be analysed based on the laboratory measured values in the meal test.

The endpoint will be analysed using an ANOVA model including treatment and region as factors and 1-hour PPG increment at baseline as covariate. The superiority will be evaluated based on the comparison of mealtime faster-acting insulin aspart and mealtime NovoRapid®.

#### ***Sensitivity analysis***

To investigate the sensitivity of the analysis with regard to the handling of missing data, a sensitivity analysis based on a pattern mixture model will be made, using the FAS. This analysis is motivated by the fact that withdrawals due to non-eligibility can reasonable be assumed to be MCAR. Multiple copies (100 copies) of the full dataset will be generated by imputing missing values based on estimated parameters as follows:

- For each of the 100 copies of the dataset, an ANOVA model with treatment and region as factors and baseline 1-hour PPG increment as a covariate is fitted to the change in 1-hour PPG increment at week 26 for the mealtime NovoRapid® group only. The estimated parameters, and their variances, from this model are used to impute missing values at week 26 for subjects in all treatment groups. However, subjects withdrawn due to withdrawal criteria 1, 2, 3 and 4 in the mealtime faster aspart group will have their imputations based on parameters estimated from the mealtime faster aspart group.
- For each of the complete data sets, the change from baseline to week 26 is analysed using an ANOVA model with treatment and region as factors, and baseline 1-hour PPG increment as a covariate.
- The estimates and standard deviations for the 100 data sets are pooled to one estimate and associated standard deviation using Rubin's formula. From this, the pooled estimates and 95% confidence interval for the treatment difference is calculated.

### **Change from baseline in 1,5-Anhydroglucitol after 26 weeks of treatment (step 4)**

Change from baseline in 1,5-anhydroglucitol after 26 weeks of treatment will be analysed based on all planned post-baseline measurements until or at 26 weeks using a MMRM for repeated measurements, similar to the model used for analysis of the primary endpoint except with baseline

1,5-anhydroglucitol as covariate. The superiority will be evaluated based on the comparison of mealtime faster-acting insulin aspart and mealtime NovoRapid®.

The sensitivity of the analysis will be addressed using the pattern mixture models described in section [17.3](#). Only the sensitivity analyses 5) and 6) in section [17.3](#) will be applied excluding the analyses where the non-inferiority margin of 0.4% are added to subjects withdrawing in the faster-acting insulin aspart arm.

### **Change from baseline in HbA1c after 26 weeks of treatment (step 5)**

Step 5 in the hierarchical testing procedure is to confirm superiority of HbA1c after 26 weeks of treatment with mealtime faster-acting insulin aspart compared to NovoRapid®. The statistical analysis will be identical to the primary analysis. Superiority will be confirmed if the upper boundary of the two-sided 95% confidence interval of the mean treatment difference (mealtime faster-acting insulin aspart minus mealtime NovoRapid®) is below 0%.

The sensitivity of the analysis will be addressed using the pattern mixture models as described in section [17.3](#). Only the sensitivity analyses 5) and 6) in section [17.3](#) will be applied excluding the analyses where the non-inferiority margin of 0.4% are added to subjects withdrawing in the faster-acting insulin aspart arm.

#### **17.4.2 Supportive secondary endpoints**

##### **17.4.2.1 Efficacy endpoints**

###### **Change from baseline in FPG after 26 weeks of treatment**

Change from baseline in FPG after 26 weeks of treatment will be analysed based on all planned post-baseline measurements until or at 26 weeks using an MMRM similar to the model used for analysis of the primary endpoint, except with baseline FPG as covariate.

###### **HbA1c responder after 26 weeks of treatment:**

###### ***HbA1c < 7.0%***

A dichotomous (responder/non-responder) endpoint will be defined based on whether a subject has met the ADA HbA1c target (HbA1c <7.0%) after 26 weeks of treatment.

This responder endpoint will be analysed based on a logistic regression model using treatment and region as factors, and baseline HbA1c as covariate. Predicted values from the model used for the primary analysis will be used for all subjects with no HbA1c at the last visit.

### ***HbA1c < 7.0% without severe hypoglycaemia***

A dichotomous (responder/non-responder) endpoint will be defined based on whether a subject has met the ADA HbA1c target (HbA1c <7.0%) after 26 weeks of treatment without treatment emergent severe hypoglycaemic episodes. The withdrawals from their randomised treatment will be set to non-responders. This is based on the assumption that the subjects would experience a severe hypoglycaemia after the withdrawal. A predicted value from the model used for the primary analysis will be used if a treatment completer does not have HbA1c at the last visit.

This responder endpoint will be analysed based on a logistic regression model using treatment and region as factors and baseline HbA1c as covariate.

### ***HbA1c < 7.0% without severe hypoglycaemia and minimal weight gain (<3.0%)***

A dichotomous (responder/non-responder) endpoints will be defined based on whether a subject has met the ADA HbA1c target (HbA1c <7.0%) after 26 weeks of treatment without treatment emergent severe hypoglycaemic episodes, and minimal weight gain from baseline to 26 weeks of treatment (defined as less than a 3% increase). The withdrawals from their randomised treatment will be set to non-responders. This is based on the assumption that the subjects would experience a severe hypoglycaemia after the withdrawal. A predicted value from the MMRM model will be used if a treatment completer does not have HbA1c or body weight at the last visit.

This responder endpoint will be analysed based on a logistic regression model using treatment and region as factors and baseline HbA1c and baseline body weight as covariates. **Change from baseline in 30- min, 1- hour, 2- hour, 3- hour and 4- hour PPG and 30- min, 2- hour, 3- hour and 4- hour PPG increment after 26 weeks of treatment (meal test)**

Laboratory measured PG from the meal test will be analysed for 30, 60, 120, 180, and 240 minutes PPG separately. The corresponding PPG increments will be derived separately using each PPG measurement minus the pre-prandial PG.

Change from baseline after 26 weeks of treatment in PPG and PPG increment endpoints will be analysed separately using an ANOVA model including treatment and region as factors, and the corresponding baseline value as covariate.

### ***Change from baseline in 7-9-7-point SMPG profile after 26 weeks of treatment:***

In general, analyses will be based on the entire 7-9-7-point profile except for the analyses of nocturnal endpoints where information in the 9-point profile will be utilised. Duration of main meals and time of injection of bolus insulin, which will be collected in connection with 7-9-7 point profiles, will be summarised descriptively.

### ***Mean of the 7-9-7-point profile***

The mean of the 7-9-7-point profile is defined as the area under the curve profile divided by the measurement time, and is calculated using the linear trapezoidal technique.

Change from baseline in mean of the 7-9-7-point profile will be analysed based on all planned post-baseline measurements until or at 26 weeks using a MMRM similar to the model used for analysis of the primary endpoint and the corresponding baseline value as covariate.

### ***PPG and PPG increment (mean, breakfast, lunch, main evening meal)***

PPG and PPG increments based on the 7-9-7-point profiles will be derived separately for PG measurements made at 1 hour. In the following section this distinction will be considered implicit and without further explanation.

PPG will be recorded by the patient as part of two 7-point and one 9-point SMPG profile prior to the visits. Individual mean mealtime PPG (post-breakfast, post-lunch, post-main evening meal) will be derived from the three profiles. Overall mean PPG will be derived from the individual derived mealtime PPG values.

PPG increment for each meal (breakfast, lunch, main evening meal) will be derived from the 7-point and 9-point profile as the difference between PPG values and the PG value before meal in each separate profile. The mean of the derived increments will then be calculated separately for each meal. Mean 1 hour PPG increments over all meals will be derived as the mean of all corresponding mean meal increments.

Change from baseline in PPG and PPG increment endpoints (mean and each separate meal) will be analysed based on all planned post-baseline measurements until or at 26 weeks using a MMRM similar to the model used for analysis of the primary endpoint and the corresponding baseline value as covariate.

### ***Fluctuation in 7-9-7-point profile***

The fluctuation in the 7-9-7-point profile is defined as:

$$\frac{1}{T} \int_0^T |PG(t) - \bar{PG}| dt ,$$

where  $T$ ,  $PG(t)$  and  $\bar{PG}$  denotes the length of the profile, the PG value at time  $t$  and the mean of the profile, respectively.

Fluctuation in the 7-9-7-point profile will be logarithmically transformed and analysed in the same way as mean of the profile is analysed with log-transformed baseline values.

### ***Change in the nocturnal SMPG measurements***

Change in nocturnal PG values will be assessed by considering the differences between PG values available at bedtime, at 4 AM and the before breakfast value the following day: (4 AM PG value minus at bedtime PG value), (before breakfast PG value minus at bedtime PG value) and (before breakfast PG value minus 4 AM PG value).

Change in the nocturnal SMPG measurements will be analysed in the same way as mean of the profile is analysed.

### ***PPG responders (overall mean of daily PPG measurements in SMPG) after 26 weeks of treatment:***

#### ***Overall PPG (1 hour) $\leq$ 7.8 mmol/L [140 mg/dL]***

A dichotomous endpoint will be defined based on whether a subject has reached an overall mean 1-hour PPG  $\leq$ 7.8 mmol/L [140 mg/dL] after 26 weeks of treatment, where PPG is derived from the 7- and 9-point profile.

This responder endpoint will be analysed based on a logistic regression model using treatment and region as factors, and baseline overall mean 1-hour PPG as covariate. Predicted values from the MMRM model for overall mean 1-hour PPG will be used for all subjects with no PPG at the last visit.

#### ***Overall PPG (1 hour) $\leq$ 7.8 mmol/L [140 mg/dL] without severe hypoglycaemia***

A dichotomous endpoint will be defined based on whether a subject has reached an overall mean 1-hour PPG  $\leq$ 7.8 mmol/L [140 mg/dL] after 26 weeks of treatment without any treatment emergent severe hypoglycaemic episodes. The withdrawals from their randomised treatment will be set to non-responders. This is based on the assumption that the subjects would experience a severe hypoglycaemia after the withdrawal. A predicted value from the MMRM model will be used if a treatment completer does not have overall mean 1-hour PPG at the last visit.

This responder endpoint will be analysed based on a logistic regression model using treatment and region as factors, and baseline overall mean 1-hour PPG as covariate.

#### ***Overall PPG (1 hour) $\leq$ 7.8 mmol/L [140 mg/dL] and HbA1c $<$ 7.0% and minimal weight gain ( $<3.0\%$ ) without severe hypoglycaemia***

A dichotomous endpoint will be defined based on whether a subject has reached an overall mean 1-hour PPG  $\leq$ 7.8 mmol/L [140 mg/dL], have HbA1c  $<$ 7.0% and has had minimal weight gain

(increase in body weight from baseline <3.0%) after 26 weeks of treatment, and without any treatment emergent severe hypoglycaemic episodes. The withdrawals from their randomised treatment will be set to non-responders. This is based on the assumption that the subjects would experience a severe hypoglycaemia after the withdrawal. A predicted value from the MMRM model will be used if a treatment completer does not have overall mean 1-hour PPG, HbA1c or body weight at the last visit.

This responder endpoint will be analysed based on a logistic regression model using treatment and region as factors, and baseline overall mean 1-hour PPG, baseline HbA1c and baseline body weight as covariates.

#### **Insulin dose (basal insulin dose, total and individual meal insulin dose) after 26 weeks of treatment**

Basal and bolus insulin doses will be recorded throughout the trial. The insulin doses will be summarised descriptively by treatment week according to regimen, both by time point of administration and as total daily dose in units and units/kg (total daily and separately for each mealtime dose).

#### **Change from baseline in lipids-lipoproteins profile after 26 weeks of treatment (total cholesterol, high density lipoproteins, low density lipoproteins)**

Change from baseline in lipid endpoints (total cholesterol, HDL and LDL) after 26 weeks of treatment will be analysed based on all planned post-baseline measurements until or at 26 weeks using an MMRM similar to the model used for analysis of the primary endpoint, except with the corresponding baseline measurement as covariate.

##### **17.4.2.2 Safety endpoints**

###### **Number of AEs during 26 weeks of treatment**

AEs will be coded using the Medical Dictionary for Regulatory Activities (MedDRA). All AEs occurring during the 26 weeks of treatment will be presented based on system organ class and preferred terms.

A Treatment Emergent Adverse Event (TEAE) is defined as an event that has an onset date on or after the first day of exposure to randomised treatment, and no later than seven days after the last day of treatment.

TEAEs are summarised descriptively, whereas AE's not defined as treatment emergent are presented in listings, including AEs reported in the 30-day follow-up period. The summaries of TEAEs are made displaying the number of subjects with at least one event, the percentage of subjects with at least one event, the number of events and the event rate per 100 patient years of

exposure. These summaries are done by seriousness, severity, relation to insulin treatment, relation to device, withdrawal due to AEs and outcome.

Furthermore, summary tables based on system organ class and preferred terms are made for:

- all TEAEs
- serious TEAEs
- possibly or probably related TEAEs
- severe TEAEs
- TEAEs with preferred term that are experienced by at least 5% of the subjects in any treatment arm or by at least 5% of all subjects

For AEs where additional information is recorded, this will be summarised and listed.

AEs occurring during the run-in period are considered non treatment emergent and will be summarised separately.

### **Number of injection site reactions**

Treatment emergent injection site reactions occurring during the trial will be summarised and listed. No formal statistical analysis will be made.

### **Classification of Hypoglycaemia:**

Treatment emergent: hypoglycaemic episodes will be defined as treatment emergent if the onset of the episode occurs on or after the first day of IMP administration after randomisation and no later than one day after the last day on IMP.

Nocturnal hypoglycaemic episodes: are episodes occurring between 00:01 and 05.59 both inclusive.

[figure not shown]
Hypoglycaemic episodes are classified according to the Novo Nordisk classification of hypoglycaemia (see [Figure 17-1](#) and the ADA classification of hypoglycaemia [Figure 17-2](#)).

### **Novo Nordisk classification of hypoglycaemia**

In normal physiology, symptoms of hypoglycaemia occur below a PG level of 3.1 mmol/L (56 mg/dL). Therefore, Novo Nordisk has included hypoglycaemia with PG levels below this cut-off point in the definition of BG confirmed hypoglycaemia.

Novo Nordisk uses the following classification ([Figure 17-1](#)) in addition to the ADA classification:

- Severe hypoglycaemia according to the ADA classification.
- Symptomatic BG confirmed hypoglycaemia: An episode that is BG confirmed by plasma glucose value  $<3.1$  mmol/L (56 mg/dL) **with** symptoms consistent with hypoglycaemia.
- Asymptomatic BG confirmed hypoglycaemia: An episode that is BG confirmed by plasma glucose value  $<3.1$  mmol/L (56 mg/dL) **without** symptoms consistent with hypoglycaemia.
- Severe or BG confirmed symptomatic hypoglycaemia: An episode that is severe according to the ADA classification or BG confirmed by a plasma glucose value  $<3.1$  mmol/L (56 mg/dL) **with** symptoms consistent with hypoglycaemia.
- BG confirmed hypoglycaemia: An episode that is BG confirmed by a plasma glucose value  $<3.1$  mmol/L (56 mg/dL) **with or without** symptoms consistent with hypoglycaemia.
- Severe or BG confirmed hypoglycaemia: An episode that is severe according to the ADA classification or BG confirmed by a plasma glucose value  $<3.1$  mmol/L (56 mg/dL) **with or without** symptoms consistent with hypoglycaemia.

[figure not shown]

Note: Glucose measurements are performed with capillary blood calibrated to plasma equivalent glucose values

Figure 17–1 Novo Nordisk classification of hypoglycaemia

### ADA classification of hypoglycaemia

- Severe hypoglycaemia: An episode requiring assistance of another person to actively administer carbohydrate, glucagon, or take other corrective actions. Plasma glucose concentrations may not be available during an event, but neurological recovery following the return of plasma glucose to normal is considered sufficient evidence that the event was induced by a low plasma glucose concentration.
- Asymptomatic hypoglycaemia: An episode not accompanied by typical symptoms of hypoglycaemia, but with a measured plasma glucose concentration  $\leq 3.9$  mmol/L (70 mg/dL).
- Documented symptomatic hypoglycaemia: An episode during which typical symptoms of hypoglycaemia are accompanied by a measured plasma glucose concentration  $\leq 3.9$  mmol/L (70 mg/dL).
- Pseudo-hypoglycaemia: An episode during which the person with diabetes reports any of the typical symptoms of hypoglycaemia with a measured plasma glucose concentration  $> 3.9$  mmol/L (70 mg/dL) but approaching that level.
- Probable symptomatic hypoglycaemia: An episode during which symptoms of hypoglycaemia are not accompanied by a plasma glucose determination but that was presumably caused by a plasma glucose concentration  $\leq 3.9$  mmol/L (70 mg/dL).

Note: Glucose measurements are performed with capillary blood calibrated to plasma equivalent glucose values

Figure 17–2 ADA classification of hypoglycaemia

Data on treatment emergent hypoglycaemic episodes are presented in terms of the number of subjects with at least one event (N), the percentage of subjects with at least one event (%), the number of events (E) and the event rate per 100 years of exposure (R). Separate summaries are made by severity considering all episodes, nocturnal and daytime episodes using Novo Nordisk and ADA classified episodes. Episodes will also be summarised overall and by category in relation to time since start of meal, as occurring during first 1, 2, and 4 hours after start of meal, and from 2 hours (exclusive) to 4 hours (inclusive) after start of meal, respectively.

The number of treatment emergent severe or BG confirmed hypoglycaemic episodes (all, daytime, nocturnal, 1 hour, 2 hour, 4 hour and from 2 hours [exclusive] to 4 hours [inclusive] after start of meal) will be analysed using a negative binomial regression model with a log-link function and the logarithm of the time period for which a hypoglycaemic episode is considered treatment emergent as offset. The model will include treatment and region as factors. To the extent where data allow, separate analyses will be performed for severe episodes.

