#### Key safety assessments

- Hypoglycaemic episodes (nocturnal and day-time)
- Adverse events (AEs)

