## 5 Trial design

### 5.1 Type of trial

This is a phase 3b, 26-week, multicentre, multinational, partly double-blind, randomised, active controlled, treat-to-target, three-armed parallel trial with an 8-week run-in period comparing the efficacy and safety of faster-acting insulin aspart with NovoRapid®, both in combination with insulin degludec in a basal-bolus regimen. The trial includes two blinded dosing arms - mealtime faster-acting insulin aspart and mealtime NovoRapid® and an open-label postmeal faster-acting insulin aspart dosing arm. See [Figure 5–1](#).

The total duration of the trial is approximately 40 weeks divided into the following periods:

- An approximate 2-week screening period
- An 8-week run-in period primarily for optimisation of the basal insulin and subject training
- A 26-week treatment period
- An 30-day follow-up period

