**Figure 5–1 Trial design**

The trial includes a screening period followed by weekly visits/phone contacts during the trial. At Visit 2 all eligible subjects will be enrolled in an 8-week run-in period and start treatment with NovoRapid® and insulin degludec. After the run-in period, subjects with an HbA1c ≤ 9.5% (80 mmol/mol) will be randomised (1:1:1) to mealtime NovoRapid® or to receive either mealtime faster-acting insulin aspart or postmeal faster-acting insulin aspart in addition to insulin degludec.

All subjects will have a standardised meal test at baseline (Visit 10) and at end of treatment (Visit 36). The meal test will be described in more details in section [8.3.1](#).

After the 26-week treatment period, each subject will have a 30-day safety follow-up period.

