### **8.4.1.1 Hypoglycaemic episodes**

Plasma glucose should always be measured and recorded when a hypoglycaemic episode is suspected.

All plasma glucose values:

- $\leq 3.9$  mmol/L (70 mg/dL) or
- $> 3.9$  mmol/L (70 mg/dL) occurring in conjunction with hypoglycaemic symptoms

should be reported in the eDiary according to the instructions below throughout the trial from Visit 2 to Visit 37.

Upon onset of a hypoglycaemic episode the subject is recommended to measure plasma glucose every 15 minutes until the SMPG value is  $>3.9$  mmol/L (70 mg/dL) or symptoms have been resolved in accordance to current guidelines [26](#).

A SMPG value  $\leq 3.9$  mmol/L (70 mg/dL) or hypoglycaemic symptoms must trigger a hypoglycaemic episode form to be completed by the subject. Repeated SMPG measurements and/or symptoms will per default be considered as one hypoglycaemic episode until a succeeding measurement is  $> 3.9$  mmol/L (70 mg/dL) and/or symptoms have been resolved. One hypoglycaemic episode form is to cover these measurements and/or symptoms. However, each hypoglycaemic episode form will cover a period of maximum 60 minutes after onset of a hypoglycaemic episode.

In case of several low SMPG values within 60 minutes, the lowest value is the one that will be reported as the SMPG value for the hypoglycaemic episode but the start time of the episode will remain as the time for the first SMPG value and/or symptom.

The e-diary will automatically link multiple values within 60 minutes to the same hypoglycaemic episode. If a new low SMPG value is measured or the subject still has symptoms more than 60 minutes after the first reported low SMPG value and/or symptom it is considered as a new episode and a new hypoglycaemic episode form is to be filled in.

The record should include the following information:

- Start date and time of the hypoglycaemic episode
- The plasma glucose value before treating the episode (if available) and any follow up measurements.

The lowest value measured during the hypoglycaemic episode will be reported as the plasma glucose value for the episode, the remaining values will be kept as source data.

- Whether the episode was symptomatic (Yes/No)

A hypoglycaemic episode starting without symptoms should be updated to symptomatic if the subject experiences symptoms later during the episode. The subjects are therefore to be prompted whether there are changes to symptoms for each low SMPG value within the 60 minutes period.

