### General considerations

In general, for endpoints evaluated as a change from baseline and/or where a baseline adjustment is made, baseline is defined as information collected at the randomisation visit (Visit 10). In case a measurement is not available at the randomisation visit, the most recent measurement prior to the randomisation visit will be used as baseline.

*Two observation periods are defined, “in-trial” and “on-treatment”, and it will be specified which period each analysis will use.*

- *In-trial: the observation period from date of randomisation and until last trial-related subject-site contact. The in-trial observation period includes data collected after treatment discontinuation.*
- *On-treatment: the observation period from date of first dose of NovoRapid®/faster-acting insulin aspart and no later than 7 days after the day of last dose of NovoRapid®/faster-acting insulin aspart. The on-treatment observation period includes data collected up to and including 7 days after treatment discontinuation.*

*Analyses of efficacy endpoints will be based on the full analysis set (FAS). All efficacy endpoints will be summarised and analysed using the full analysis set (FAS), unless otherwise stated. Safety endpoints will be summarised using the safety analysis set (SAS) and analysed using the FAS.*

*Presentation of results from a statistical analysis will include the estimated mean treatment effects (LSMeans) for change from baseline, if applicable. Estimated mean treatment differences (or ratios) will be presented together with two-sided 95% confidence intervals for all endpoints analysed statistically.*

*For endpoints measured over time mean values will be plotted to explore the trajectory over time. For survival endpoints, e.g. drop-out pattern, Kaplan-Meier plots are presented for each treatment. Data collected before randomisation will only be summarised descriptively.*

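### The hypoglycaemia rate models leave out each subject's recorded run-in rate: the analysis is valid, but its intervals are wider than they need to be

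*Protocol*

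**What the plan says.** Protocol section 17.4.2.2, in the paragraph after the ADA classification, specifies a "negative binomial regression model with a log-link function" with log treatment-emergent time as offset. It covers seven counts of severe or BG confirmed episodes: all, daytime, nocturnal, and four windows after the start of a meal (1, 2 and 4 hours, and 2 to 4 hours). Severe episodes are analysed separately if the data allow. On covariates it says: "The model will include treatment and region as factors". Amendment 2 (2.29.4.2) revises other parts of this section but not this paragraph.

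The run-in information comes from three places:

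- Section 5.1 provides "An 8-week run-in period primarily for optimisation of the basal insulin and subject training".
- The text under Figure 5–1 has all eligible subjects "start treatment with NovoRapid® and insulin degludec" at Visit 2.
- Section 8.4.1.1 says that qualifying glucose values "should be reported in the eDiary according to the instructions below throughout the trial from Visit 2 to Visit 37".

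The general considerations in section 17, retained in Amendment 2, add: "Data collected before randomisation will only be summarised descriptively".

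Hypoglycaemia is listed among the key safety assessments in the summary. In section 4.2.2.2, including its Amendment 2 wording, it is a supportive secondary safety endpoint.

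**The concern.** Hypoglycaemia counts usually differ widely between subjects. When events are not rare, that spread largely sets the width of the rate-ratio interval. A subject's own rate over 8 weeks on a common regimen is a natural predictor of the later rate. It is fixed before allocation and already in the database. The modelled continuous efficacy endpoints and body weight each carry their own baseline value as a covariate; this model carries no counterpart.

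What is at stake is precision. The protocol reports ratios with two-sided 95% intervals, so a wider interval makes it harder either to see or to rule out a difference in hypoglycaemia. Section 3.3 gives this some point: an earlier trial found a significantly higher rate with faster aspart in the first hour after a meal, though not overall.

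**Working it through.** **Figure to reproduce.** There is none. The protocol states no rate, dispersion, power or interval width for hypoglycaemia; its power figures concern HbA1c only.

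**Inputs from the documents.** 333 subjects per arm (999 randomised 1:1:1), 8-week run-in, 26-week treatment period, and treatment discontinuation possibly as low as 8%.

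**Assumed inputs.** Episode rate, between-subject spread, and the correlation between a subject's log rates in run-in and treatment.

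**Why a predictor of the rate helps.** For a negative binomial comparison of two arms of n subjects, with mean count μ and dispersion k, approximately

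Var(log rate ratio) ≈ (2/n) × (1/μ + k).

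A baseline predictor lowers k and leaves 1/μ alone. Take 20 episodes per patient-year: μ = 20 × 26/52.18 = 9.97, so 1/μ = 0.100, and 2/333 = 0.00601. The k values below are fitted values from simulation with log-normal subject rates, between-subject dispersion about 1, and 8% stopping early.

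| Model | k | SE by formula | Simulated SE | 95% limits, × or ÷ |
|---|---|---|---|---|
| Planned | 0.68 | √(0.00601 × 0.780) = 0.068 | 0.0690 | 1.145 |
| Run-in rate added, correlation 0.5 | 0.59 | √(0.00601 × 0.690) = 0.064 | 0.0652 | 1.136 |
| Run-in rate added, correlation 0.75 | 0.46 | √(0.00601 × 0.560) = 0.058 | 0.0594 | 1.124 |

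The SE ratios are 0.945 and 0.862. The adjusted model would match the planned precision with 333 × 0.945² = 297 or 333 × 0.862² = 247 subjects per arm.

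**Range over rates.** In the same simulation at correlations 0.5 to 0.75, the SE falls by 2–6% at 5 episodes per patient-year, 6–14% at 20 and 8–20% at 50. With correlation 0 nothing is gained or lost.

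A second set uses an SD of log rate of 0.9 and correlations of 0.4 to 0.8:

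| Episodes per patient-year | Fall in SE |
|---|---|
| 50 | 5–25% |
| 20 | 4–18% |
| 5 | 2–8% |

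At 50 per patient-year the SE goes from 0.0688 to 0.0651 at correlation 0.4 (1 − 0.0651/0.0688 = 5%). It goes from 0.0688 to 0.0521 at correlation 0.8 (24%, the top of the range within simulation error). The 95% limits go from ×/÷ 1.144 (e^(1.96 × 0.0688)) to 1.136 and 1.108.

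**Sparse subsets.** Here 1/μ dominates. For a window holding 5% of episodes at an overall 20 per patient-year, μ = 0.05 × 9.97 = 0.50 and 1/μ = 2.0, so lowering k matters less. With the all-episode run-in rate as covariate and overall rates of 20 to 50, the SE falls by about 1–11% when the window's share of episodes also varies between subjects.

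**Severe episodes.** At an assumed 0.2 per patient-year, μ = 0.10 and 1/μ = 10. Adding the run-in rate of the same episodes changes the SE by 0.1% or less.

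**The case against.** The strongest reply is that nothing here is invalid. Treatment, region and an exposure offset make a sound model for a randomised comparison. Hypoglycaemia is outside the testing hierarchy, the sample size is set on the first two HbA1c steps, and no decision rule depends on this interval. That stands. It makes this an efficiency point and not an error.

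The gain is also modest on the scale a reader sees: at 20 episodes per patient-year the limits move from ×/÷ 1.145 to between 1.136 and 1.124. The first hour after a meal, where interest is greatest, is described in section 3.3 as a smaller fraction of episodes, so it is among the cases that gain least.

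The run-in is not a stable baseline either. Subjects change insulins at Visit 2, basal insulin is titrated weekly while bolus is adjusted only for safety, and all receive carbohydrate-counting training. After randomisation the emphasis moves to bolus titration (sections 5.3 to 5.3.2 and 8.6.2). All this can weaken the correlation, so 0.8 is optimistic.

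Three stronger readings are tempting, and the documents do not support them:

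- **Bias.** Randomisation protects the planned estimate, and under a log link the rate ratio has the same target with or without the covariate.
- **The trial's main safety comparison.** The protocol calls hypoglycaemia a key safety assessment and a supportive secondary endpoint, no more.
- **A ban on using run-in data.** The section 17 sentence "Data collected before randomisation will only be summarised descriptively" cannot exclude baseline covariates. The same section takes the latest measurement before randomisation as baseline when Visit 10 is missing. The Visit 10 meal test, completed before randomisation under section 8.3.1, also supplies the covariate for hierarchical step 3.

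Nor is the contrast with change-from-baseline endpoints a contradiction: an episode count is not such an endpoint.

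**Conclusion.** The point holds as a precision gain that needs no new data. The covariates are fixed in the protocol, the run-in counts are recorded for every randomised subject, and the model does not use them. The comparison stays valid; its intervals are wider than needed to the extent that the run-in rate predicts the later one.

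Under 5 to 50 episodes per patient-year and correlations of 0.4 to 0.8, the standard error falls by about 2–25%. The fall is about 1–11% for sparse meal windows and near zero for severe episodes. Direction is well supported; size is not, because rates, spread and correlation are all assumed. The change in titration between run-in and treatment argues for the lower part of the range.

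**What to change.** In the section 17.4.2.2 models for severe or BG confirmed episodes, add the covariate log((run-in severe or BG confirmed episodes + 0.5) / run-in time), with run-in time counted from Visit 2 to Visit 10. The 0.5 handles zero counts. For the sparse meal windows use this all-episode run-in rate, because a window-specific run-in count would be too thin to predict much.

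Bolus adjusting method may be added for consistency with the other models revised in Amendment 2; no precision gain is claimed for it. The section 17 sentence on data collected before randomisation needs at most a clause saying that it does not exclude baseline covariates.

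The cost is one derived variable and one or two sentences, to be settled before database lock. If the correlation proves low, virtually nothing is lost.
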